2. Continuous QL catheter is more beneficial than single shot QL block or intrathecal morphine after 24 hours in providing post-operative pain control.
3. Our exploratory hypothesis is that after 48 hours a QL catheter would continue to reduce morphine consumption until 72 hours.

Primary outcome measure

Total narcotic consumption in morphine equivalents (in milligrams) for the first 72 hours after surgery will be calculated. Total narcotic used in the spinal anesthetic will be excluded.

XIII. Secondary objectives

1. Total narcotic usage at 24 and 48 hours will be assessed in morphine equivalents. Intraoperative consumption of opioids will be excluded.
2. Time to first analgesic request
3. Numeric pain score (NPS)- static and dynamic at 6, 12, 24, 48 and 72 hours
4. Pruritus at 24, 48 and 72 hours
5. Nausea at 24, 48 and 72 hours
6. Vomiting at 24, 48 and 72 hours
7. Sedation at 24, 48 and 72 hours
8. Patient satisfaction- quality of sleep, ability to ambulate, and ability to breast feed and take care of newborn at 24, 48 and 72 hours

Secondary outcome measures-

1. Total narcotic consumption in morphine equivalents (in milligrams) at 12, 24 and 48 hours will be measured.

Time after CS	Total morphine equivalents (mg)
At 4 hours	
At 6 hours	
At 12 hours	

At 24 hours	
At 72 hours	

2. Time to first analgesic request will be reviewed from the chart
3. Our research personnel will use NPS. This will be assessed at 6, 12, 24, 48 and 72 hours. NPS is a 11-point scale as shown below. The study patient will verbally select a numerical value that best corresponds with the pain the patient is experiencing at that point. This data will be statistically analyzed. Static and dynamic pain scores will be assessed. Dynamic pain scores will be assessed by asking the patient to sit up in bed from supine to sitting at 6 hours. This will be repeated at 12, 24, 48 and 72 hours however if patient is ambulating, dynamic pain score during ambulation will be assessed.

No pain

Distressing pain

Worst pain

No pain (0)

Mild pain (1,2,3)

Moderate pain (4,5,6)

Severe pain (7,8,9,10)

Time interval after CS	NPS (static)	NPS (dynamic)
At 6 hours		
At 12 hours		
At 24 hours		
At 48 hours		
At 72 hours		

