Placement of QL catheters- A 20 G peripheral nerve polyamide catheter (Contiplex® Ultra 360™ continuous nerve block set, B Braun, Bethlehem, PA, USA) will be inserted through the 18 G echogenic needle under direct ultrasound visualization. The catheter will be secured using the standard technique employed at our institution. Correct placement of QL catheters will be confirmed by injecting saline under ultrasound guidance. QL catheter will be placed on both sides in a similar fashion. A member of the research team who performed the initial QLB in the operating room will attach a peripheral nerve pump (CADD® Solis ambulatory infusion pump, Minneapolis, MN, USA) to the QL catheter once the patient reaches the post anesthesia care unit (PACU). No infusion will be initiated if the patient is assigned to group 1 (Spinal anesthesia with ITM + US guided QLB single shot sham block + QLB catheters with no continuous infusion) and group 2 (Spinal anesthesia without ITM + US guided QLB single shot with bupivacaine hydrochloride + QLB catheters with no continuous infusion). Infusion of 0.2 % ropivacaine at 10 ml/hour on each side will be initiated if the patient is randomized to group 3 (Spinal anesthesia without ITM + US guided QLB single shot with bupivacaine hydrochloride + QLB catheters infusing 0.2% ropivacaine hydrochloride). A member of our research team who is blinded to the group allocation will manage all peripheral nerve catheters. No extra bolus medication will be given through any of the catheters. We are not initiating any infusion through the peripheral nerve catheters in group 1 and 2 to avoid the possibility of pain due to stretching of muscles and facial planes by normal saline.

All patients will be started on a multimodal pain regimen. They will receive scheduled acetaminophen 1000 mg orally and ibuprofen 600 mg every 6 hours. Oxycodone 2.5 mg-5 mg oral every 4 hours as needed will be added for breakthrough pain. Patients will be

evaluated by the anesthesia pain service for adding a PCA with intravenous hydromorphone if pain not adequately controlled on their regimen.

Our research personnel who will be blinded, will follow up patients for the first 48 hours to collect data listed under primary and secondary objectives. We are not assessing dermatomal levels to determine the spread of local anesthetic as it could possibly result in patients and study personnel knowing which group they fall under and potentially unblinding the study.

XVII. Conduct

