
1. Screening

Our research team will assess patients for eligibility based on the inclusion criteria. We will obtain informed written consent from all eligible patients. Any member of our research team at any point will obtain this consent during the preoperative period (anesthesia clinic, surgery clinic, preoperative holding area). Patients will be given adequate time to consult with family members and use the internet for additional information. All questions and concerns by the patient will be addressed at this point.

Once a written informed consent is obtained the patient will be educated about the study protocol, NPS assessment, other assessment tools and the use of MMP medications. Baseline pain score will be recorded at this point. A complete preoperative evaluation, physical examination and preoperative testing will be conducted per usual protocol by the anesthesiologist caring for the patient.

Three copies will be made of the written informed consent. Patient will be given a copy of the signed written informed consent. A copy of the consent will be placed in the patient's chart. Our research team will keep one copy of the consent.

2. Enrollment

Patient will be enrolled if all inclusion, exclusion criteria are met and the patient has provided an informed written consent. Our research coordinator will then randomly assign the patient into one of the groups based on the random allocation software.

3. Randomization and allocation concealment

Anesthesiologist in the operating room will not be blinded to the patient's randomization, as they must prepare the spinal with or without intrathecal morphine and the prescribed solution for block placement. Anesthesiologist performing the regional nerve block not be blinded as they will have to perform a

sham QLB or a QLB with the study drug. All other research personnel collecting data or seeing the patient postoperatively will not know what the contents of the spinal medication were, whether or not the QLB contained no drug or bupivacaine, or whether the QLB catheter infusions contain no drug or ropivacaine.

Patient's assigned group will be communicated to the anesthesiologist caring for the patient in an opaque envelope so that no other research personnel are wise to the assignment.

Research personnel responsible for randomizing and assigning group will not be the same personnel as those evaluating the patient or collecting data.

4. Preoperative assessment

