The data will be analyzed within one month after completion of data collection for all enrolled patients. The deidentified data will be uploaded to PI's UTH-Share account and shared with the statistician. We will conduct Kolmogorov-Smirnov test to test normal distribution. Continuous variables will be summarized as mean and standard deviation for each group. Comparisons between any two groups will be evaluated by two-sample t test. If a variable has skewed distribution, we will report median and inter-quartile range and use Wilcoxon rank sum test for two-sample comparison. Incidences of side effects and patient satisfaction scales will be summarized as frequency and percentage for each group. Their association with intervention arm will be evaluated by Fisher's exact test. P values less than 0.05 will be considered as significant. Test and confidence interval are equivalent methods. SD is needed in calculating a confidence interval. The test is equivalent to obtaining a 90% confidence interval and comparing the upper limit of confidence interval to δ . All statistical analyses will be performed by using the SAS software (version 9.4, the SAS Institute, Cary, NC).

XX. Ethics

1. Informed consent- An informed, voluntary consent will be obtained systematically. Once the patient meets inclusion criteria, a member of our research team will speak with the patient about the study. Information will be provided regarding all study drugs, intervention and post-operative care. Standard treatment options will also be provided. Adequate time will be provided so that the patient can consult with family members, friends or look up more information using the internet.
2. Privacy and confidentiality- The patient will be linked with a study number. Only specific computers will be used by our research team to store patient information. All data will be restricted to team members, institutional review board (IRB) and FDA. Health insurance portability and accountability act (HIPPA) will be strictly followed.
3. Risk vs benefits- Major risks involved with this study are unintentional disclosure of patient information and adverse effect due to the local anesthetic leading to LAST. There is no monetary benefit involved with this study. Patient will benefit from adequate pain control with this intervention.

XXI. Study timeline

Recruitment of sample size- 9 months

Data collection and analysis- 3 months

No long-term follow up is needed with this study.

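### The recorded baseline pain score has no role in the pain analysis, which amounts to 24–30 unadjusted pairwise tests rather than a longitudinal model with contrasts matched to the hypotheses

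*Combined protocol and SAP*

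**What the plan says.** - **Baseline.** Section XVII.1 (Screening): "Baseline pain score will be recorded at this point". The moment is not fixed, because the score follows consent and "Any member of our research team at any point will obtain this consent during the preoperative period", whether in a clinic or in preoperative holding. It is not labelled static or dynamic.
- **Pain outcomes.** Section XIII lists the numeric pain score as a secondary objective, "static and dynamic at 6, 12, 24, 48 and 72 hours", and repeats under the outcome measures: "This will be assessed at 6, 12, 24, 48 and 72 hours".
- **Follow-up.** Section XVI says that blinded personnel "will follow up patients for the first 48 hours to collect data listed under primary and secondary objectives". The follow-up table (XVII.5) and the first enrollment-termination criterion (XVII.6) also stop at 48 hours. Section XV gives each patient 72 hours, or less on earlier discharge.
- **Dynamic task.** The patient sits up at 6 hours; this is repeated later, "however if patient is ambulating, dynamic pain score during ambulation will be assessed" (Section XIII).
- **Analysis.** Section XIX: "Comparisons between any two groups will be evaluated by two-sample t test". For skewed variables the plan will "use Wilcoxon rank sum test for two-sample comparison". Significance is p < 0.05. No covariate, repeated-measures method, key time point or multiplicity rule is named.

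**The concern.** A pain score is collected before treatment and then left out of every comparison. If it predicts later pain, precision is given away in arms of 25. The plan also has no method for a score measured repeatedly in the same patient. Read as it stands, each score is compared at each time for each pair of arms, so isolated significant results are likely by chance and nothing says which of them matter. A patient discharged before the last assessment simply drops out of the comparison at that time, although her earlier scores carry information about it.

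**Working it through.** **The plan's own figures.** None is given for pain scores; Section XIX sizes the trial on opioid use. Those figures reproduce by noncentral t:
- Hypothesis 1: means 10 and 27, margin 5, so shift 22; SD 25, 23 per group, one-sided 0.05: power 90.2% (stated 90%).
- Hypothesis 2: difference 29, SD 23, 15 per group, two-sided 0.05: power 91.5% (stated 91.5%).
- Both at 23 per group: 0.902 × 0.987 = 0.890 (stated 89.4%, by simulation).

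None of these involves pain scores, so nothing below touches the sample size.

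**Number of tests.** 2 scores × 3 pairs × 5 times = 30; with four times, 2 × 3 × 4 = 24. Expected false positives if no arm differs: 30 × 0.05 = 1.5, or 24 × 0.05 = 1.2. The chance of at least one, simulated with 25 per arm and a common correlation between scores in the same patient (assumed, since none is given):

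| Correlation | 15 tests (one score) | 30 tests |
|---|---|---|
| 0.3 | 45% | 66% |
| 0.5 | 38% | 56% |
| 0.7 | 33% | 44% |

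The 24-test figure lies between the two columns. With independent tests the chance would be 1 − 0.95^24 = 71% or 1 − 0.95^30 = 79%.

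**Baseline adjustment.** With 75 patients in three arms, the variance of an arm difference at one time, relative to no adjustment, is (1 − r²) × (1 + 1/70). The difference detectable with 80% power is 0.809 SD for the planned pairwise t test.

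| r (assumed) | Variance ratio | Detectable difference (SD) |
|---|---|---|
| 0 | 1.014 | 0.809 |
| 0.1 | 1.004 | 0.805 |
| 0.2 | 0.974 | 0.793 |
| 0.3 | 0.923 | 0.772 |
| 0.5 | 0.761 | 0.701 |

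Break-even is r = √(1/71) ≈ 0.12. If 80–90% of baseline scores were 0 (an assumption), an underlying correlation of 0.3–0.5 would fall to about 0.17–0.35 and the variance reduction, before the covariate's cost, to 3–12%.

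**Partial data.** If a share m miss the last visit at random given earlier scores, and the within-patient correlation is r, the model's last-visit variance relative to complete cases is (1 − r²) + r²(1 − m). With m = 0.1 and r = 0.3 this is 0.991; with m = 0.5 and r = 0.7 it is 0.755. The reduction is thus 1–25%, entirely on assumed inputs.

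**Which contrast to test.** Hypothesis 2 expects a catheter benefit after 24 hours. Suppose it is present only at 48 and 72 hours.
- *Average over all five times:* the effect shrinks to 2/5 = 0.40. The standard error falls to √((1 + 4ρ)/5), which is 0.77 at ρ = 0.5 and 0.87 at ρ = 0.7. Signal-to-noise becomes 0.40/0.77 = 0.52 or 0.40/0.87 = 0.46. A difference with 80% power at one late time has about 25–30% power on this average.
- *Average over 48 and 72 hours only:* the effect is kept in full. The standard error falls to √((1 + ρ)/2) = 0.87 or 0.92, so signal-to-noise rises by a factor of 1/0.87 = 1.15 or 1/0.92 = 1.09.

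**The case against.** The strongest case against is that the gain is unproven and the model has a price.

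- **Baseline may predict little.** Chronic pain is an exclusion (Section XI), the time of the score varies, and no correlation is given. This stands: the gain may be close to nil. The possible loss, however, is no more than about 1.4% in variance.
- **A longitudinal model is not free precision.** With complete data, an arm-by-time model without baseline gives the same differences at each time as separate analyses. This stands. Any gain comes from baseline, pooled degrees of freedom, partial records and well-chosen contrasts.
- **The scale and the task.** The score is bounded at 0–10 and the plan itself allows for skew. The dynamic task may change from sitting up to walking, possibly in a way that depends on treatment. Both points stand and call for a sensitivity analysis and cautious reading.
- **Testing one time at a time is an inference.** Section XIX does not say so in words. It offers nothing else for a repeated score, so the reading is fair, but it is a reading.

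A reader might also infer that a single arm difference averaged over all times should become the test. The documents point the other way: the hypotheses in Section XII separate the first 24 hours from the time after, and the overall average dilutes an effect confined to the later period. It would also leave six unadjusted tests (three pairs, two scores), with a simulated 17–22% chance of at least one false positive. Nor do the documents support adjusting opioid consumption for baseline pain; nothing in them links the two.

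**Conclusion.** The point holds as a modest improvement to a secondary analysis. The baseline score is collected and unused, and the pain comparisons are pairwise, unadjusted and without a rule for 24 to 30 tests. Including baseline changes the variance of an arm difference by between about +1.4% (r = 0) and −24% (r = 0.5), with −8% at r = 0.3. These figures assume 25 per arm and the same r at each time. The benefit from partial records assumes data missing at random.

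Three stronger readings go too far. The change does not come at no cost, since it brings model assumptions and uses a degree of freedom. The count is not firmly 30 while the documents disagree on 48 or 72 hours. And the primary outcome and the sample size are not in question, because both rest on opioid consumption.

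**What to change.** 1. Reconcile Section XIII (pain scores to 72 hours) with Sections XVI, XVII.5 and XVII.6 (follow-up to 48 hours) before specifying any model.
2. For static and for dynamic pain separately, prespecify a longitudinal model with arm, time, arm-by-time and the baseline pain score as covariate, including every patient with at least one post-operative score.
3. Name the contrasts in advance: single-shot block versus intrathecal morphine over 6, 12 and 24 hours; catheter versus single-shot block, and catheter versus intrathecal morphine, after 24 hours (48 and 72 hours, or 48 only, as step 1 settles). Do not test an average over all times.
4. The model does not control multiplicity by itself. Three contrasts on two scores are still six tests, so name one score as key, apply an adjustment such as Holm, or label the results supportive. Report all other time-specific differences with confidence intervals as description. No margin for pain scores is given, so a non-significant early contrast must not be read as equivalence.
5. Keep a rank-based or ordinal sensitivity analysis for skew. Record which task produced each dynamic score and interpret that outcome with caution.
6. State when the baseline score is taken and whether it is static or dynamic.

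The cost is a few lines in Section XIX, a mixed-model run in the SAS version already named, one degree of freedom for the covariate and the model's assumptions. No extra patients or visits are needed. The wording should be fixed before unblinding.

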The data will be analyzed within one month after completion of data collection for all enrolled patients. The deidentified data will be uploaded to PI's UTH-Share account and shared with the statistician. We will conduct Kolmogorov-Smirnov test to test normal distribution. Continuous variables will be summarized as mean and standard deviation for each group. Comparisons between any two groups will be evaluated by two-sample t test. If a variable has skewed distribution, we will report median and inter-quartile range and use Wilcoxon rank sum test for two-sample comparison. Incidences of side effects and patient satisfaction scales will be summarized as frequency and percentage for each group. Their association with intervention arm will be evaluated by Fisher's exact test. P values less than 0.05 will be considered as significant. Test and confidence interval are equivalent methods. SD is needed in calculating a confidence interval. The test is equivalent to obtaining a 90% confidence interval and comparing the upper limit of confidence interval to δ . All statistical analyses will be performed by using the SAS software (version 9.4, the SAS Institute, Cary, NC).

XX. Ethics

1. Informed consent- An informed, voluntary consent will be obtained systematically. Once the patient meets inclusion criteria, a member of our research team will speak with the patient about the study. Information will be provided regarding all study drugs, intervention and post-operative care. Standard treatment options will also be provided. Adequate time will be provided so that the patient can consult with family members, friends or look up more information using the internet.
2. Privacy and confidentiality- The patient will be linked with a study number. Only specific computers will be used by our research team to store patient information. All data will be restricted to team members, institutional review board (IRB) and FDA. Health insurance portability and accountability act (HIPPA) will be strictly followed.
3. Risk vs benefits- Major risks involved with this study are unintentional disclosure of patient information and adverse effect due to the local anesthetic leading to LAST. There is no monetary benefit involved with this study. Patient will benefit from adequate pain control with this intervention.

XXI. Study timeline

Recruitment of sample size- 9 months

Data collection and analysis- 3 months

No long-term follow up is needed with this study.

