Early oral intake, mobilization, removal of urinary catheter are all important components of the enhanced recovery after surgery protocol (ERAS). We hypothesize that by performing QL blocks post CS the amount of pain, narcotic consumption will be reduced significantly. Early ambulation will help prevent deep vein thrombosis. Performing QL blocks will also minimize side effects secondary to ITM and will facilitate ERAS and better patient satisfaction scores.

A recent study conducted by Salama et al concluded that QLB (without ITM) provided lower numeric rating scores at rest and during movement when compared to the group that received ITM (without QLB). Time to first morphine dose was also longer in the QLB. This study concluded that a longer duration of analgesia and reduced postoperative morphine consumption was achieved with QLB when compared to ITM.(Salama 2019)

X. Sample size

25 in each group

Total number of enrolled patients: 75

XI. Study population

Inclusion criteria

1. Age greater than 18 years
2. Elective C section via Pfannenstiel incision
3. Living singleton pregnancy
4. Gestation week at least 37 weeks
5. ASA status 1, 2 and 3

6. Primary and secondary C sections

Exclusion criteria

1. Chronic pain
2. Opioid tolerant patients
3. Allergy to drugs used in the study.
4. Cognitive dysfunction
5. BMI > 40
6. Coagulation disorder
7. Local infection
8. Inability to tolerate oral medication
9. Previous intra-abdominal surgery
10. Patients who will receive a combined spinal epidural for their C section
11. Local anesthetics injected at any other fascial plane except the QLB plane (for e.g.- local wound infiltration by surgeon)
12. Patients who received sedation or general anesthesia during their CS (midazolam, ketamine, fentanyl, propofol, hydromorphone)

Voluntary patient withdrawal from the study- patient has right to withdraw at any point during the study period

Withdrawal in case of unexpected events- This will be determined by the investigators.

XII. Primary objective

Primary objective of the study is to compare opioid consumption in morphine equivalents between the groups that received postoperative analgesia with intrathecal morphine versus US guided QL blocks versus US guided QL catheters

Our working hypothesis is-

1. Single shot QL block is equivalent to intrathecal morphine with less side effects in providing post-operative pain control for the first 24 hours.

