4. Numeric scale to rate side effects (SE) of pruritus, nausea, vomiting and sedation at 24, 48 and 72 hours; 0- no side effects 10- extremely severe side effect possible. This numeric scale is a 11-point scale as shown below. The study patient will verbally select a numerical value that best corresponds with the side effects the patient is experiencing at that point. This data will be statistically analyzed.

No SE

Distressing SE

Worst SE

No SE (0)

Mild SE (1,2,3)

Moderate SE (4,5,6)

Severe SE (7,8,9,10)

Side effects	Scale at 24 hours	Scale at 48 hours	Scale at 72 hours
Pruritus			
Nausea			
Vomiting			
Sedation			

5. Patient satisfaction will be measured on a Likert scale (5 points) at 48 and 72 hours. How satisfied were you with the following?

	Extremely satisfied	Very satisfied	Moderately satisfied	Slightly satisfied	Not satisfied
Quality of sleep					
Ability to ambulate					
Ability to breast feed/ formula feed					
Ability to take care of new born					

XIV. Study drugs

1. Preservative free morphine
2. Normal saline
3. Bupivacaine hydrochloride 0.25 %
4. Ropivacaine hydrochloride 0.1 % XV.

Study schedule

Expected start date for enrolling patients

Expected end date for enrolling patients

Enrollment period for each patient- 72 hours, earlier if discharged.

XVI. Study design

This is a prospective double-blinded randomized control trial performed at a single institution.

Screened patients meeting inclusion criteria will be randomized into three groups:

Group 1- Spinal anesthesia with ITM + US guided QLB single shot sham block + QLB catheters with no continuous infusion

Group 2- Spinal anesthesia without ITM + US guided QLB single shot with bupivacaine hydrochloride + QLB catheters with no continuous infusion

Group 3- Spinal anesthesia without ITM + US guided QLB single shot with bupivacaine hydrochloride + QLB catheters continuously infusing 0.2% ropivacaine hydrochloride

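### Fisher's exact test ignores the order in the satisfaction items, and can also waste power on side effects, depending on how incidence is defined

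*Combined protocol and SAP*

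**What the plan says.** Section XIII (secondary outcome measures, item 4) collects side effects as scores: "Numeric scale to rate side effects (SE) of pruritus, nausea, vomiting and sedation at 24, 48 and 72 hours". The anchors are "0- no side effects 10- extremely severe side effect possible". Four bands are printed with the scale: 0, 1-3, 4-6 and 7-10. Item 5 collects satisfaction on four items: "Patient satisfaction will be measured on a Likert scale (5 points) at 48 and 72 hours".

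Section XIX, under the statistical analysis plan, gives one analysis for both: "Incidences of side effects and patient satisfaction scales will be summarized as frequency and percentage for each group". The next sentence reads "Their association with intervention arm will be evaluated by Fisher's exact test". It states no cut-point for incidence, no time point and no use of the bands.

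Just before this comes a general rule for continuous variables: "If a variable has skewed distribution, we will report median and inter-quartile range and use Wilcoxon rank sum test for two-sample comparison". It is not tied to the side-effect scores or the satisfaction items.

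Side effects also appear in working hypothesis 1 (section XII): "Single shot QL block is equivalent to intrathecal morphine with less side effects in providing post-operative pain control for the first 24 hours".

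**The concern.** Fisher's exact test takes the response categories as unordered. Its p-value adds up the probabilities of all tables with the same margins that are no more likely than the observed one. Shuffling the columns leaves that sum unchanged, so the ranking from not satisfied to extremely satisfied contributes nothing. A treatment that moves patients one step along the scale is judged as if the five labels were arbitrary.

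For side effects, if incidence means any score above zero, the severity that the instrument was built to record is not tested either.

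The sponsor wants to say that the block gives fewer side effects and better satisfaction. The trial is small and states no power for these outcomes. A needlessly weak test makes it more likely that a real difference is reported as none.

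**Working it through.** **Sample size.** The plan's own figures were reproduced first, to fix the n.
- Hypothesis 1: the distance to the margin is 5 - (10 - 27) = 22 and the standard error is 25 x sqrt(2/23) = 7.37. The ratio is 2.98, and a one-sided 5% t-test has 90.2% power (plan: 90%).
- Hypothesis 2: (49 - 20) / (23 x sqrt(2/15)) = 29/8.40 = 3.45, which gives 91.5% two-sided (plan: 91.5%).
- Both hypotheses at 23 per group: 0.902 x 0.987 = 0.890 (plan: 89.4%).

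The figures agree. The comparison below uses the plan's 23 per arm (25 enrolled, to allow for drop-out) and 5% two-sided. The two-sided level is an assumption.

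**Satisfaction, two arms.** Three baseline distributions over the five levels were assumed: 5/10/25/35/25%, 20% in each, and 2/5/13/30/50%. The second arm was shifted by proportional odds: logit P(Y <= j) in arm B = logit P(Y <= j) in arm A + log(OR). For example, with the first baseline and OR 3, the cumulative 5% becomes (0.05/0.95 x 3) / (1 + 0.05/0.95 x 3) = 0.136, and the whole distribution becomes 14/21/32/23/10%. Each cell rests on 2,000 simulated trials, with a Monte Carlo error of about 1 point.

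| Odds ratio | Fisher 2x5 | Wilcoxon |
|---|---|---|
| 1 (size) | 4-5% | 4-5% |
| 2 | 14-15% | 24-25% |
| 3 | 32-33% | 51-54% |
| 4 | 49% | 71-72% |
| 5 | 61-65% | 83-84% |

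The ranges run over the three baselines. Within a baseline the gap runs from about 10 points (15.4% against 25.0% at OR 2) to about 23 (60.7% against 83.4% at OR 5).

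**Satisfaction, three arms.** Fisher's test on the 3x5 table was compared with Kruskal-Wallis for two of these baselines (1,000 trials, error about 1.6 points). For odds ratios 1/2/4 the power is 37-38% against 60-61%. For 1/4/4 it is 50-53% against 74-75%.

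**Side effects, two arms.** The proportion affected and the severity among those affected are both assumed. Percentages with a v are incidences in the two arms.

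| Assumed change | Fisher, any/none | Fisher, four bands | Wilcoxon, 0-10 |
|---|---|---|---|
| None (size) | 2% | 4% | 4% |
| 70% v 50%, severity lower | 19% | 67% | 70% |
| 80% v 60%, severity lower | 21% | 76% | 86% |
| 70% v 40%, severity lower | 44% | 76% | 85% |
| Incidence only, 70% v 40% | 43% | 38% | 44% |
| Incidence only, 80% v 40% | 73% | 67% | 69% |
| Severity only, 80% v 80% | 2.5% | 87% | 74% |
| Severity only, 60% v 60% | 2.5% | 73% | 30% |

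Three patterns follow:
- Any/none loses heavily once severity moves: 70 - 19 = 51 points in the first scenario. It loses nothing material when only incidence moves.
- The four bands lose about 2 to 10 points when incidence changes.
- The bands beat the rank sum test when only severity changes, because the tied zeros, equally common in both arms, dilute the ranks.

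**The case against.** The strongest objection concerns side effects. A reader might infer that a score of 1 will count the same as a 10. The documents do not say so. Incidence has no stated cut-point, and the four bands printed with the scale are a natural basis for a frequency table. That reading keeps severity, though not its order, and the loss is then small or reversed. The general rule on skewed variables could also be read to cover the 0-10 scores, with incidence reported in addition. Against this, the sentence that names side effects assigns them to Fisher's test and to nothing else. What stands is an undefined analysis that may or may not be costly.

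A reader might also infer that power is always lost. It is not: if treatment changes only the proportion affected, the two tests are about equal. The large side-effect figures depend on the severity drop chosen. With mean severity about 6 against 3.5 among those affected, incidence 70% against 50% and 25 per arm, the contrast is 24% against 88%. This shows how far the assumption sets the size.

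Nor would the choice of test alone explain a missed difference. At odds ratio 2.5 with 23 per arm, the rank sum test reaches only about 39% on satisfaction, against about 22% for Fisher's. The trial was not sized for these outcomes.

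Finally, hypothesis 1 mentions side effects, but the sample size section confirms it by non-inferiority of opioid consumption alone. A reader should not conclude that the primary conclusion or its power is at risk. None of these objections touches the satisfaction items, where Fisher's test is the only one named and the loss appears under every distribution tried.

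**Conclusion.** The point holds for satisfaction and holds conditionally for side effects.

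For satisfaction, ignoring order costs about 10 to 23 points of power with 23 per arm for odds ratios 2 to 5. This assumes a proportional-odds shift and the three baselines above. The documents give no distribution, so these are illustrations rather than predictions.

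For side effects, the plan can lose much of its power if incidence means any versus none and treatment also lowers severity. It loses little if only incidence changes, and little or nothing if the four bands are used.

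Fisher's test keeps its error rate, so no conclusion is biased. These are secondary outcomes, and the sample size and primary power do not change. It is a free improvement in efficiency, not a correction of an error.

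**What to change.** In the statistical analysis plan:
- Compare the four satisfaction items and the 0-10 side-effect scores with an ordinal method. This can be the Wilcoxon rank sum test for named pairwise contrasts (for example single-shot QL block against ITM, the contrast in hypothesis 1), Kruskal-Wallis for all three arms, or proportional-odds regression reporting an odds ratio with its confidence interval.
- Keep frequencies and percentages as description, and say whether the four printed severity bands are used for them.
- Keep Fisher's test only for a yes/no side-effect incidence, and state its cut-point and time point.

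The cost is SAP wording only. The scores are already to be collected, the rank sum test is already in the plan, and no patient, visit or form is added. Where only incidence changes, the rank sum test gave up at most about 4 points in the scenarios tried (69% against 73%). The retained yes/no analysis covers that case.
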